10.1.5 Data Quality Assurance

All patient data relating to the study will be recorded on electronic CRFs unless transmitted to the Sponsor or designee electronically (e.g., laboratory data). The Investigator is responsible for verifying that data entries are accurate and correct by electronically signing the CRF.

The Investigator must maintain accurate documentation (source data) that supports the information entered in the eCRF.

The Investigator must permit study-related monitoring, audits, IRB/IEC review, and Regulatory Agency inspections and provide direct access to source data documents.

The Sponsor or designee is responsible for the data management of this study including quality checking of the data.

The Sponsor assumes accountability for actions delegated to other individuals (e.g., contract research organizations).

Study monitors will perform ongoing source data verification to confirm that data entered into the eCRF by authorized site personnel are accurate, complete, and verifiable from source documents; that the safety and rights of patients are being protected; and that the study is being conducted in accordance with the currently approved protocol and any other study agreements, ICH GCP, and all applicable regulatory requirements.

Records and documents, including signed ICFs, pertaining to the conduct of this study must be retained by the Investigator for 2 years after study completion unless local regulations or institutional policies require a longer retention period. No records may be destroyed during the retention period without the written approval of the Sponsor. No records may be transferred to another location or party without written notification to the Sponsor.

Data entered in the eCRF that are transcribed from source documents must be consistent with the source documents or the discrepancies must be explained. The Investigator may need to request

Version 3.0 62 of 85 20 April 2022

previous medical records or transfer records, depending on the study. Also, current medical records must be available.

The specific procedures to be used for data entry and query resolution using the eCRF will be provided to study sites in a training manual. In addition, site personnel will receive training on the eCRF.

10.1.6 Source Documents

Source documents provide evidence for the existence of the patient and substantiate the integrity of the data collected. Source documents are filed at the Investigator's site.

Data reported in the eCRF that are transcribed from source documents must be consistent with the source documents or the discrepancies must be explained. The Investigator may need to request previous medical records or transfer records, depending on the study. Also, current medical records must be available.

The Investigator must maintain accurate documentation (source data) that supports the information entered in the eCRF.

Study monitors will perform ongoing source data verification to confirm that data entered into the eCRF by authorized site personnel are accurate, complete, and verifiable from source documents; that the safety and rights of patients are being protected; and that the study is being conducted in accordance with the currently approved protocol and any other study agreements, ICH GCP, and all applicable regulatory requirements.

10.1.7 Study and Site Start and Closure

First Act of Recruitment

The study start date is the date on which the clinical study will be open for recruitment of patients.

The first act of recruitment is the first site open and will be the study start date.

Study/Site Termination

The Sponsor or designee reserves the right to close the study site or terminate the study at any time for any reason at the sole discretion of the Sponsor. Study sites will be closed upon study completion. A study site is considered closed when all required documents and study supplies have been collected and a study site closure visit has been performed.

Version 3.0 63 of 85 20 April 2022

The Investigator may initiate study site closure at any time, provided there is reasonable cause and sufficient notice is given in advance of the intended termination.

Reasons for the early closure of a study site by the Sponsor or Investigator may include but are not limited to:

- Failure of the Investigator to comply with the protocol, the requirements of the IRB/IEC or local health authorities, the Sponsor's procedures, or GCP guidelines.
- Inadequate recruitment of patients by the Investigator.
- Total number of patients included earlier than expected.
- Discontinuation of further study treatment development.

If the study is prematurely terminated or suspended, the Sponsor shall promptly inform the Investigators, the IECs/IRBs, the regulatory authorities, and any contract research organization(s) used in the study of the reason for termination or suspension, as specified by the applicable regulatory requirements. The Investigator shall promptly inform the patient and should assure appropriate patient therapy and/or follow-up.

10.1.8 Protocol Approval and Amendment

Before the start of the study, the study protocol and/or other relevant documents will be approved by the IEC/IRB/Competent Authorities, in accordance with local legal requirements. The Sponsor must ensure that all ethical and legal requirements have been met before the first patient is enrolled in the study.

This protocol is to be followed exactly. To alter the protocol, amendments must be written, receive approval from the appropriate personnel, and receive IRB/IEC/Competent Authority approval prior to implementation (if appropriate). In the US: Following approval, the protocol amendment(s) will be submitted to the Investigational New Drug Application under which the study is being conducted.

Administrative changes (not affecting the patient benefit/risk ratio) may be made without the need for a formal amendment. All amendments will be distributed to all protocol recipients, with appropriate instructions.

10.1.8.1 Access to Source Data

During the study, a monitor will make site visits to review protocol compliance, compare eCRF entries and individual patient's medical records, assess drug accountability, and ensure that the

Version 3.0 64 of 85 20 April 2022

study is being conducted according to pertinent regulatory requirements. The eCRF entries will be verified with source documentation. The review of medical records will be performed in a manner to ensure that patient confidentiality is maintained.

Checking of the eCRF entries for completeness and clarity, and cross-checking with source documents, will be required to monitor the progress of the study. Moreover, regulatory authorities of certain countries, IRBs, IECs, and/or the Sponsor's Clinical QA Group may wish to carry out such source data checks and/or on-site audit inspections. Direct access to source data will be required for these inspections and audits; they will be carried out giving due consideration to data protection and medical confidentiality. The Investigator assures the Sponsor of the necessary support at all times.

Version 3.0 65 of 85 20 April 2022

10.2 Appendix 2: Clinical Laboratory Tests

- All clinical laboratory tests should be done after patients have fasted for at least 8 hours.
- The tests will be performed by the central laboratory, unless prior approval is received from the Sponsor.
- Protocol-specific requirements for inclusion or exclusion of patients are details in Sections 5.1 and 5.2.
- Additional tests may be performed at any time during the study as determined necessary by the Investigator or required by local regulations.
- Investigators must document their review of each laboratory safety report.

Table 6 Protocol-required Safety Laboratory Tests

Laboratory Tests	Parameters	
Hematology	Platelet count	WBC count with differential:
	RBC count	Neutrophils
	Hemoglobin	Lymphocytes
	Hematocrit	Monocytes
	RBC indices:	Eosinophils
	Mean corpuscular volume (MCV)	Basophils
	Mean corpuscular hemoglobin (MCH)	
	% Reticulocytes	
Clinical chemistry	BUN	AST/SGOT
	Potassium	Total and direct bilirubin
	Creatinine	ALT/SGPT
	Sodium	Total protein
	Glucose, fasting	Alkaline phosphatase
	Calcium	Chloride
	Phosphorus	Albumin
	Bicarbonate	

Version 3.0 66 of 85 20 April 2022

Routine urinalysis	Specific gravity pH, glucose, protein, blood, ketones, by dipstick Microscopic examination (if blood or protein is abnormal)
Pregnancy testing	Highly sensitive serum and/or urine hCG pregnancy test (as needed for women of childbearing potential) at timepoints detailed in Section 8.3.5.
Other screening tests	HbA1c and TSH will be done at Screening only Follicle-stimulating hormone and estradiol (as needed in women of non-childbearing potential only) Urine alcohol and drug screen (to include at minimum: amphetamines, barbiturates, cocaine, opiates, THC and benzodiazepines) Serology (HIV antibody, hepatitis B surface antigen (HbsAg), and HCV antibody) [HCV PCR will be done for any HCV Ab positive result] All study required laboratory assessments will be performed by a central laboratory.

NOTES:

1. Local urine testing will be standard for the protocol unless serum testing is required by local regulation or IRB/IEC.

ALT= alanine aminotransferase; AST= aspartate aminotransferase; BUN=blood urea nitrogen; hCG= human chorionic gonadotropin; HCV = hepatitis C; HIV = human immunodeficiency virus; IEC= independent ethics committee; INR= international normalized ration; IRB= institutional review board; RBC= red blood cell; SGOT= serum glutamic-oxaloacetic transaminase; SGPT= serum glutamic-pyruvic transaminase; THC = tetrahydrocannabinol; TSH = thyroid stimulating hormone; WBC= white blood cell.

Version 3.0 67 of 85 20 April 2022

10.3 Appendix 3: AEs and SAEs: Definitions and Procedures for Recording, Evaluating, Follow-up, and Reporting

10.3.1 Definition of AE

AE Definition

An AE is any untoward medical occurrence in a patient or clinical study patient, temporally associated with the use of a study treatment, whether or not considered related to the study treatment.

NOTE: An AE can therefore be any unfavorable and unintended sign (including an abnormal laboratory finding), symptom, or disease (new or exacerbated) temporally associated with the use of a study treatment.

Events Meeting the AE Definition

Any abnormal laboratory test results (hematology, clinical chemistry, or urinalysis) or other safety assessments (e.g., ECG, radiological scans, vital signs measurements), including those that worsen from baseline, considered clinically significant in the medical and scientific judgment of the Investigator (e.g., not related to progression of underlying disease).

Exacerbation of a chronic or intermittent pre-existing condition including either an increase in frequency and/or intensity of the condition.

New condition detected or diagnosed after study treatment administration even though it may have been present before the start of the study.

Signs, symptoms, or the clinical sequelae of a suspected treatment-treatment interaction.

Signs, symptoms, or the clinical sequelae of a suspected overdose of either study treatment or a concomitant medication. Overdose per se will not be reported as an AE/SAE unless it is an intentional overdose taken with possible suicidal/self-harming intent. Such overdoses should be reported regardless of sequelae.

Lack of efficacy or failure of expected pharmacological action per se will not be reported as an AE or SAE. Such instances will be captured in the efficacy assessments. However, the signs,

Version 3.0 68 of 85 20 April 2022

symptoms, and/or clinical sequelae resulting from lack of efficacy will be reported as AE or SAE if they fulfill the definition of an AE or SAE.

Events NOT Meeting the AE Definition

Any clinically significant abnormal laboratory findings or other abnormal safety assessments that are associated with the underlying disease, unless judged by the Investigator to be more severe than expected for the patient's condition.

The disease/disorder being studied or expected progression, signs, or symptoms of the disease/disorder being studied, unless more severe than expected for the patient's condition.

Medical or surgical procedure (e.g., endoscopy, appendectomy): the condition that leads to the procedure is the AE.

Situations in which an untoward medical occurrence did not occur (social and/or convenience admission to a hospital).

Anticipated day-to-day fluctuations of pre-existing disease(s) or condition(s) present or detected at the start of the study that do not worsen.

10.3.2 Definition of SAE

An SAE is an AE that:

a. Results in death

b. Is life-threatening

The term *life-threatening* in the definition of *serious* refers to an event in which the patient was at risk of death at the time of the event. It does not refer to an event, which hypothetically might have caused death, if it were more severe.

Version 3.0 69 of 85 20 April 2022

c. Requires inpatient hospitalization or prolongation of existing hospitalization

In general, hospitalization signifies that the patient has been admitted (usually involving at least an overnight stay) at the hospital or emergency ward for observation and/or treatment that would not have been appropriate in the physician's office or outpatient setting. Complications that occur during hospitalization are AE. If a complication prolongs hospitalization or fulfills any other serious criteria, the event is serious. When in doubt as to whether hospitalization occurred or was necessary, the AE should be considered serious.

Hospitalization for elective treatment of a pre-existing condition that did not worsen from baseline is not considered an AE.

d. Results in persistent or significant disability/incapacity

The term disability means a substantial disruption of a person's ability to conduct normal life functions.

This definition is not intended to include experiences of relatively minor medical significance such as uncomplicated headache, nausea, vomiting, diarrhea, influenza, and accidental trauma (e.g., sprained ankle) that may interfere with or prevent everyday life functions but do not constitute a substantial disruption.

e. Is a congenital anomaly/birth defect

f. Other situations

Medical or scientific judgment should be exercised by the Investigator in deciding whether SAE reporting is appropriate in other situations such as significant medical events that may jeopardize the patient or may require medical or surgical treatment to prevent one of the other outcomes listed in the above definition. These events should usually be considered serious.

Examples of such events are intensive treatment in an emergency room or at home for allergic bronchospasm; blood dyscrasias or convulsions that do not result in hospitalization; or development of drug dependency or drug abuse.

Version 3.0 70 of 85 20 April 2022

10.3.3 Recording and Follow-up of AE and SAE

AE and SAE Recording

When an AE/SAE occurs, it is the responsibility of the Investigator to review all documentation (e.g., hospital progress notes, laboratory, and diagnostics reports) related to the event.

The Investigator will then record all relevant AE/SAE information.

It is **not** acceptable for the Investigator to send photocopies of the patient's medical records to the Sponsor in lieu of completion of the AE/SAE eCRF page.

There may be instances when copies of medical records for certain cases are requested by the Sponsor. In this case, all patient identifiers, with the exception of the patient number, will be blinded on the copies of the medical records before submission to the Sponsor.

The Investigator will attempt to establish a diagnosis of the event based on signs, symptoms, and/or other clinical information. In such cases, the diagnosis (not the individual signs/symptoms) will be documented as the AE/SAE.

Assessment of Intensity

The clinical severity of an AE will be graded using the NCI CTCAE Version 5.0.

The severity of all adverse events should be graded according to the Common Terminology Criteria for Adverse Events (CTCAE) v.5.0. These criteria can be found at http://ctep.cancer.gov/reporting/ctc.html. For those adverse event terms not listed in the CTCAE, the following grading system should be used:

- *CTCAE Grade 1:* Mild; asymptomatic or mild symptoms; clinical or diagnostic observations only; intervention not indicated.
- CTCAE Grade 2: Moderate; minimal local or noninvasive intervention indicated; limiting age-appropriate instrumental activities of daily living.

Version 3.0 71 of 85 20 April 2022

- CTCAE Grade 3: Severe or medically significant but not immediately life-threatening; hospitalization or prolongation of hospitalization indicated; disabling; limiting self-care activities of daily living
- CTCAE Grade 4: Life threatening consequences; urgent intervention indicated.
- CTCAE Grade 5: Death related to the adverse event.

The investigator is to evaluate whether the AE meets serious criteria. An event is defined as 'serious' when it meets at least one of the predefined outcomes as described in the definition of an SAE, NOT when it is rated as severe.

Assessment of Causality

The Investigator is obligated to assess the relationship between study treatment and each occurrence of each AE/SAE. The Investigator will use clinical judgment to determine the relationship.

A *reasonable possibility* of a relationship conveys that there are facts, evidence, and/or arguments to suggest a causal relationship, rather than a relationship cannot be ruled out.

Alternative causes, such as underlying disease(s), concomitant therapy, and other risk factors, as well as the temporal relationship of the event to study treatment administration will be considered and investigated.

The Investigator will also consult the Investigator's Brochure and/or Product Information, for marketed products, in their assessment.

For each AE/SAE, the Investigator must document in the medical notes that he/she has reviewed the AE/SAE and has provided an assessment of causality.

There may be situations in which an SAE has occurred, and the Investigator has minimal information to include in the initial report in the electronic data collection tool. However, it is very important that the Investigator always make an assessment of causality for every event before the initial transmission of the SAE data to the electronic data collection tool.

The Investigator may change their opinion of causality in light of follow-up information and send an SAE follow-up report with the updated causality assessment.

Version 3.0 72 of 85 20 April 2022

The following "binary" decision choice will be used by the Investigator to describe the initial causality assessment:

- Related: Reasonable possibility of a relatedness
- Not related: No reasonable possibility of relatedness.

The following factors should also be considered:

- The temporal sequence from study drug administration— The event should occur after the study drug is given. The length of time from study drug exposure to event should be evaluated in the clinical context of the event.
- Underlying, concomitant, intercurrent diseases— Each report should be evaluated in the context of the natural history and course of the disease being treated and any other disease the subject may have.
- Concomitant drug-
 - The other drugs the subject is taking or the treatment the subject receives should be examined to determine whether any of them might be recognized to cause the event in question.
- Known response pattern for this class of study drug-Clinical and/or preclinical data may indicate whether a particular response is likely to be a class effect.
- Exposure to physical and/or mental stresses— The exposure to stress might induce adverse changes in the recipient and provide a logical and better explanation for the event.
- The pharmacology and pharmacokinetics of the study drug-The known pharmacologic properties (absorption, distribution, metabolism, and excretion) of the study drug should be considered.

The causality assessment is one of the criteria used when determining regulatory reporting requirements.

Follow-up of AE and SAE

The Investigator is obligated to perform or arrange for the conduct of supplemental measurements and/or evaluations as medically indicated or as requested by the Sponsor to elucidate the nature and/or causality of the AE or SAE as fully as possible. This may include additional laboratory tests or investigations, histopathological examinations, or consultation with other health care professionals.

Version 3.0 73 of 85 20 April 2022

If a patient dies during participation in the study or during a recognized follow-up period, the Investigator will provide the Sponsor with a copy of any post-mortem findings including histopathology.

New or updated information will be recorded in the originally completed form.

The Investigator will submit any updated SAE data to the Sponsor within 24 hours of receipt of the information.

10.3.4 Reporting of SAE

SAE Reporting to the Sponsor via email, fax or telephone

Initial Reports

All SAEs occurring from the time of informed consent until 30 days following the last administration of study drug must be reported to Medpace Clinical Safety **within 24 hours** of the knowledge of the occurrence. After the 30-day reporting window, any SAE that the investigator considers related to study must be reported to Medpace Clinical Safety or the Sponsor/designee.

To report the SAE, complete the SAE form electronically in the electronic data capture (EDC) system for the study. When the form is completed, Medpace Safety personnel will be notified electronically by the EDC system and will retrieve the form. If the event meets serious criteria and it is not possible to access the EDC system, send an email to Medpace Safety at [contact] or call the Medpace SAE hotline (phone number listed below), and fax/email the completed paper SAE form to Medpace (contact information listed below) within 24 hours of awareness. When the EDC system becomes available, the SAE information must be entered within 24 hours of the system becoming available.

Medpace SAE hotline – USA:

[contact], dial "3" or [contact], dial "3"

[contact] or [contact]

E-mail: [contact]

Follow-Up Reports

The investigator must continue to follow the subject until the SAE has subsided or until the condition becomes chronic in nature, stabilizes (in the case of persistent impairment) or the subject dies.

Version 3.0 74 of 85 20 April 2022

Within 24 hours of receipt of follow-up information, the investigator must update the SAE form electronically in the EDC system for the study and submit any supporting documentation (e.g., subject discharge summary or autopsy reports) to Medpace Clinical Safety via fax or email. If it is not possible to access the EDC system, refer to the procedures outlined above for initial reporting of SAEs.

Version 3.0 75 of 85 20 April 2022

10.4 Appendix 4: Contraceptive Guidance and Collection of Pregnancy Information

Definitions

Woman of Childbearing Potential

A woman is considered fertile following menarche and until becoming postmenopausal unless permanently sterile (see below).

Women in the following categories are not considered WOCBP:

- 1. Premenarchal
- 2. Premenopausal female with 1 of the following:
 - Documented hysterectomy
 - Documented bilateral salpingectomy
 - Documented bilateral oophorectomy

Note: Documentation can come from the site personnel's: review of the patient's medical records, medical examination, or medical history interview.

3. Premenopausal female

- A postmenopausal state is defined as no menses for 12 months without an alternative medical cause. An FSH level in the postmenopausal range may be used to confirm a postmenopausal state in women not using hormonal contraception or hormonal replacement therapy (HRT). However, in the absence of 12 months of amenorrhea, a single FSH measurement is insufficient.
- Females on HRT and whose menopausal status is in doubt will be required to use one of the non-hormonal highly effective contraception methods if they wish to continue their HRT during the study. Otherwise, they must discontinue HRT to allow confirmation of postmenopausal status before study enrollment.

Version 3.0 76 of 85 20 April 2022

Contraception Guidance

Female Patients

Female patients of childbearing potential are eligible to participate if they agree to use a highly effective or accepted effective method of contraception consistently and correctly as described below.

Highly Effective Contraception Methods

Highly Effective Contraceptive Methods That Are User Dependent^a

Failure rate of < 1% per year when used consistently and correctly.

Combined (estrogen- and progestogen-containing) hormonal contraception associated with inhibition of ovulation

- Oral
- Intravaginal
- Transdermal

Highly Effective Contraceptive Methods That Are User Independent^a

Implantable progestogen-only hormonal contraception associated with inhibition of ovulation

- Intrauterine device (IUD)
- Intrauterine hormone-releasing system (IUS)

Bilateral tubal occlusion

Vasectomized Partner

A vasectomized partner is a highly effective contraception method provided that the partner is the sole male sexual partner of the woman of childbearing potential (WOCBP) and the absence of sperm has been confirmed. If not, an additional highly effective method of contraception should be used.

Sexual Abstinence

Sexual abstinence is considered a highly effective method only if defined as refraining from heterosexual intercourse during the entire period of risk associated with the study treatment. The reliability of sexual abstinence needs to be evaluated in relation to the duration of the study and the preferred and usual lifestyle of the patient.

Accepted Effective Contraceptive Methods

Acceptable birth control methods that result in a failure of more than 1% per year include:

• Progestogen-only oral hormonal contraception, where inhibition of ovulation is not the primary mode of action

Version 3.0 77 of 85 20 April 2022

^a Typical use failure rates may differ from those when used consistently and correctly. Use should be consistent with local regulations regarding the use of contraceptive methods for patients participating in clinical studies.

- Male or female condom with or without spermicide
- Cap, diaphragm, or sponge with spermicide
- Nonhormonal intrauterine device

A combination of male condom with either cap, diaphragm, or sponge with spermicide (double barrier methods) are also considered acceptable, but not highly effective, birth control methods.

Pregnancy Testing

At a minimum, a pregnancy test should be performed as per the SoA (Table 1).

• Women of childbearing potential (WOCBP) should only be included in the study after a confirmed menstrual period and a negative highly sensitive serum pregnancy test

Pregnancy testing will be performed whenever a menstrual cycle is missed or when pregnancy is otherwise suspected.

Collection of Pregnancy Information

Female Patients Who Become Pregnant

- The Investigator will collect pregnancy information on any female patient who becomes pregnant while participating in this study. Information will be recorded on the appropriate form and submitted to the Sponsor within 24 hours of learning of a patient's pregnancy.
- The patient will be followed to determine the outcome of the pregnancy. The Investigator will collect follow-up information on the patient and the neonate, and the information will be forwarded to the Sponsor. Generally, follow-up will not be required for longer than 6 to 8 weeks beyond the estimated delivery date. Any termination of pregnancy will be reported, regardless of fetal status (presence or absence of anomalies) or indication for the procedure.
- While pregnancy itself is not considered to be an AE or SAE, any pregnancy complication will be reported as an AE or SAE. Abnormal pregnancy outcomes (eg, spontaneous abortion, fetal death, stillbirth, congenital anomalies, ectopic pregnancy) or genetic abnormalities (whether leading to an elective abortion or not) are always considered to be SAEs and will be reported as such. Any post study pregnancy-related SAE considered reasonably related to the study treatment by the Investigator will be

Version 3.0 78 of 85 20 April 2022

reported to the Sponsor as described in Section 10.3.4. While the Investigator is not obligated to actively seek this information in former study patients, he or she may learn of an SAE through spontaneous reporting.

• Any female patient who becomes pregnant while participating in the study will discontinue study treatment or be withdrawn from the study.

Version 3.0 79 of 85 20 April 2022

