5.1 Inclusion Criteria

Patients are eligible to be included in the study only if all of the following criteria apply:

- 1. Has a documented diagnosis of moderate to severe DG or IG according to the ANMS GCSI-DD score during the Screening period (Score of >2 on average of the screening days).
- 2. Moderate to severe delay in gastric emptying rate as measured by the GEBT at Screening defined as GE half-time (t1/2) ≥ the 80th percentile of normative data as determined by Cairn Diagnostics.
- 3. Male or female patients 18 to 80 years of age, inclusive, at baseline.
- 4. Has continuous moderate to severe symptoms for gastroparesis (that is, chronic postprandial fullness, abdominal pain, postprandial nausea, vomiting, loss of appetite and/or early satiety) as assessed by the investigator for at least the past 3 months.
- 5. Has hemoglobin A1c (HbA1c) less than (<) 11 percent (%).
- 6. Has Body Mass Index range between 18 40.
- 7. Women of childbearing potential must have a negative serum pregnancy test at the Screening Visit and a negative urine pregnancy test at baseline before dosing.
- 8. Women of childbearing potential must use one of the following acceptable methods of contraception throughout the study (1 month prior to Screening through 1 month after last dose of study medication): oral contraceptive medication, intrauterine device (IUD), hormonal implants, injectable contraceptive medications, double-barrier methods, or tubal ligation.
- 9. Females who are postmenopausal (age-related amenorrhea ≥ 12 consecutive months and increased follicle-stimulating hormone [FSH] > 40 mIU/mL. If necessary, to confirm postmenopausal status, an FSH will be drawn at Screening) or who have undergone hysterectomy or bilateral oophorectomy are exempt from pregnancy testing.
- 10. Male patients must be willing to use acceptable contraceptive measures such as vasectomy or double barrier method and refrain from sexual activity with any

Version 3.0 33 of 85 20 April 2022

- female who is pregnant or lactating. Female partners of study participants are asked to use acceptable methods of contraception as listed in Inclusion #8 above.
- 11. Patient must be willing and able to swallow whole tablets.
- 12. Patient must be willing and able to comply with study procedures.

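### Appendix 4 calls women of childbearing potential eligible on a single barrier method, which inclusion criterion 8, the governing rule, does not accept

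*Combined protocol and SAP*

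**What the plan says.** Inclusion criterion 8 in Section 5.1 opens: "Women of childbearing potential must use one of the following acceptable methods of contraception throughout the study". It then names oral contraceptives, an intrauterine device and hormonal implants, and ends with "injectable contraceptive medications, double-barrier methods, or tubal ligation". The synopsis gives the same list.

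Appendix 4 (Section 10.4), under Female Patients, states its own eligibility rule: "Female patients of childbearing potential are eligible to participate if they agree to use a highly effective or accepted effective method of contraception".

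Two bullets in its accepted effective list are single barrier methods: "Male or female condom with or without spermicide" and "Cap, diaphragm, or sponge with spermicide". The sentence after the bullets reads: "A combination of male condom with either cap, diaphragm, or sponge with spermicide (double barrier methods) are also considered acceptable".

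In the highly effective group, Appendix 4 includes intravaginal and transdermal combined hormones and two conditional options: "A vasectomized partner is a highly effective contraception method provided that the partner is the sole male sexual partner" and "Sexual abstinence is considered a highly effective method only if defined as refraining from heterosexual intercourse".

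**The concern.** The protocol states who may enrol in two places, and the two do not agree. A woman whose only contraception is a condom is told by Appendix 4 that she qualifies and by criterion 8 that she does not. Neither text refers to the other, and Appendix 4 has no sentence deferring to criterion 8.

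A site that took its contraceptive rule from the appendix could randomize a woman whom Section 5.1 excludes. That would be an eligibility deviation in a trial of 24 patients, caused by the protocol's own wording. She would also be relying on one barrier where criterion 8 asks for two.

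**Working it through.** No arithmetic bears on this point, so the check is a comparison of texts.

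**Step 1: compare the lists.** The inputs are criterion 8 (Section 5.1, repeated in the synopsis) and the contraception guidance in Appendix 4. Two matchings are assumed: a hormone-releasing intrauterine system counts as an intrauterine device, and tubal occlusion counts as tubal ligation.

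| Method | Criterion 8 | Appendix 4 |
|---|---|---|
| Oral contraceptive | yes | yes (combined; progestogen-only) |
| Intrauterine device or system | yes | yes |
| Hormonal implant | yes | yes |
| Tubal ligation or occlusion | yes | yes |
| Double-barrier | yes | yes |
| Injectable | yes | not listed |
| Condom alone | no | yes |
| Cap, diaphragm or sponge with spermicide, alone | no | yes |
| Intravaginal combined hormones | no | yes |
| Transdermal combined hormones | no | yes |
| Vasectomized partner | no | yes, with conditions |
| Abstinence | no | yes, with conditions |

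Criterion 8 therefore names six methods, one of them a barrier option. The mismatch runs in both directions.

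**Step 2: do the two barrier bullets stand alone?** They could be harmless if they only listed the parts of a double barrier. The sentence that follows them rules this out. It says that the combination is acceptable as well, so each bullet is already an option in its own right.

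**Step 3: is Appendix 4 only descriptive?** No. Its lead sentence under Female Patients speaks of eligibility and ties it to both method groups.

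**Step 4: which text governs?** Section 5 requires patients to meet all inclusion criteria, and Section 5.1 makes eligibility conditional on every listed criterion. Criterion 8 is one of them, so it prevails.

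**Step 5: a test case.** Take a woman of childbearing potential who meets every other criterion and uses only a condom. Under Appendix 4 she is eligible. Under criterion 8, and so under the protocol as a whole, she is not.

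**Step 6: what limits the consequence?** The Schedule of Activities has eligibility checked at Visits 1, 2 and 3 and a pregnancy test at Visits 1, 3, 4, 5, 6 and 8, which is six visits. Appendix 4 adds a test after any missed cycle and requires a confirmed menstrual period before inclusion. Dosing lasts 28 days. Section 2.2 reports no sign of dysmorphogenic effects in rats or rabbits.

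**The case against.** The strongest reply is that the hierarchy is already settled. Section 5.1 requires every criterion. The Appendix 4 sentence cannot be a sufficient condition for entry, because it would then also waive the age, symptom and gastric emptying criteria. Criterion 8 is self-contained, is stated identically in two places and does not cite the appendix. Sections 8.2.5 and 8.3.5 send investigators to Appendix 4 only for procedures once a pregnancy is reported. A site would have to pass over a clear criterion to be misled.

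Most of this stands, and it fixes the size of the point. It does not make the Appendix 4 sentence correct: on contraception that sentence still names methods as qualifying that criterion 8 does not accept.

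A reader might go further in four ways that the documents do not support:

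- *The eligibility rule is unresolved.* It is not. Sections 5 and 5.1 decide for criterion 8.
- *Appendix 4 is laxer throughout.* It is not. It classes intravaginal and transdermal hormones, a vasectomized partner and abstinence as highly effective, while double-barrier, which criterion 8 accepts, is classed as not highly effective. Only the two single-barrier bullets point to weaker protection.
- *The mismatch can be given as a proportion of methods.* Any such ratio depends on how the list is split, for example whether cap, diaphragm and sponge are one entry or three, and a one-way count would miss the injectables.
- *Premenopausal women fall outside the childbearing-potential definition*, because the third category in Appendix 4 carries that heading. The text beneath it defines the postmenopausal state. This is a separate clerical slip and adds no weight here.

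**Conclusion.** The inconsistency is real and lies in current, operative text. Criterion 8 governs, and the Appendix 4 eligibility sentence is wrong as written.

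The severity is minor. What is at risk is an avoidable eligibility deviation and slightly weaker pregnancy protection for any woman enrolled on a single barrier. The second part assumes that one barrier protects less than two; the documents give no failure rates for individual barrier methods. How many women might be affected cannot be estimated, because the documents do not say which methods patients will use. The gastric emptying and symptom endpoints, the power statement and the planned analyses do not depend on this text.

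**What to change.** Correct the Appendix 4 eligibility sentence itself, so that no opposing sentence remains beside it. Suggested wording: *Female patients of childbearing potential are eligible only if they use one of the methods listed in inclusion criterion 8, consistently and correctly.* Then delete the two single-barrier bullets, or mark them as not sufficient alone. The new sentence also settles the other differences: injectables are covered by reference, and the four remaining Appendix 4 methods no longer confer eligibility.

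The cost is one rewritten sentence and two deleted or annotated bullets. Section 10.1.8 lets administrative changes that do not affect the benefit/risk ratio go ahead without a formal amendment; the sponsor would judge whether this edit qualifies. Procedures, sample size and analysis stay as they are.

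If the sponsor would rather accept some of the Appendix 4 methods, criterion 8 would have to be widened. That is a separate choice which changes eligibility. It would need ethics committee approval under Section 10.1.1 and possibly a revised consent form under Section 10.1.2.
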